
6. Lab values:
 
 • ANC > 1.5 x 10⁹/L • PLT > 99 x 10⁹/L • Hemoglobin > 8 g/dL • Tbili < 1.6 x ULN 
 ○ Except subjects with known Gilbert's syndrome • AST, ALT and alk phos < 2.6 x upper limit of normal (ULN) • Serum creatinine ≤ 1.5 mg/dL, or if serum creatinine is > 1.5 mg/dL, creatinine clearance must be ≥ 50 mL/min (calculate creatinine clearance using the Cockcroft-Gault formula (see Appendix D). • PR / INR and PTT ≤ 1.3 X ULN. Subjects receiving anticoagulation treatment may be allowed to participate with INR established within the therapeutic range prior to randomization 			

7. Ability to understand and the willingness to sign a written informed consent document
			

8. Patients of childbearing potential must agree to use effective contraception until at least 6 months after treatment with dabrafenib and trametinib. See exclusion criteria re pregnancy testing
			

9. Able to swallow and retain oral medication and must not have any clinically significant gastrointestinal abnormalities that may alter absorption such as malabsorption syndrome or major resection of the stomach or bowels
			

10. Left ventricular ejection fraction equal to or greater than normal within 1 month of enrollment. ECHO scans must be used throughout the study.
			

Exclusion Criteria
			

1. No prior treatment with agents targeting BRAF-mutant tyrosine kinases or MEK inhibitors or radiation of target lesions
			

2. Invasive malignancy other than ameloblastoma within 3 years, excluding curatively treated basal cell carcinoma, and other highly curable cancers such as early stage cutaneous squamous cell carcinoma (T1 NO) cervical CIS, early stage prostate cancer, thyroid cancer, breast cancer or history of malignancy with confirmed activating RAS mutation at any time			

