3. Uncontrolled hypertension (systolic blood pressure > 140 mm Hg and diastolic blood pressure of > 90 mm Hg which cannot be controlled by anti-hypertensive therapy), CHF, or other major medical illness.			
4. Prior allergic reactions attributed to compounds of similar chemical or biologic composition to dabrafenib or trametinib.			
5. Concomitant use of strong inhibitors (eg, ketoconazole, nefazodone, clarithromycin, gemfibrozil) or strong inducers (eg, rifampin, phenytoin, carbamazepine, phenobarbital, St John's wort) of CYP3A4 or CYP2C8 . For a full list of excluded drugs see Section 4.1.2 of the protocol			
6. Concomitant use of proton pump inhibitors, H2-receptor antagonists, antacids			
7. Known G6PD deficiency			
8. Pregnant or nursing patients. Women of childbearing potential must have a negative SERUM pregnancy test within 14 days of enrollment. Women of child-bearing potential must agree to use effective contraception for 14 days prior to enrollment, throughout the treatment period and for 4 to 6 months after the last dose of study treatment.			
9. EKG with QTcB (Bazett's formula) > 480 ms done within 14 days of enrollment			
10. Interstitial lung disease or pneumonitis.			
11. A history of retinal vein occlusion (RVO).			

12. Congestive heart failure NYHA Class III or worse (Marked limitation of physical activity. Comfortable at rest. Less than ordinary activity causes fatigue, palpitation, or dyspnea.)
			

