If a subject misses a dose of dabrafenib, the subject may take the dose immediately if the next dose is scheduled for at least 6 hours later. If the next scheduled dose of dabrafenib is due in less than 6 hours, the subject should skip the dose and resume dabrafenib dosing at the next scheduled dose. If a subject misses a dose of trametinib, the subject may take the dose immediately if the next dose is scheduled for at least 12 hours later.

Patients whose tumors are amenable to surgical resection will continue dosing continuously for at least 6 weeks and proceed to surgery between weeks 6 and 7, without dose interruption. Patients undergoing surgical resection will continue dabrafenib and trametinib until it is necessary to take nothing by mouth in the hours preceding surgery, but **ideally the patients will be dosed with dabrafenib and trametinib within 12 hours of the surgical resection**. Patients whose tumors are grossly completely resected will not resume dabrafenib and trametinib. Patients whose tumors are not resected completely have the option to resume the dabrafenib and trametinib at the dose they were receiving immediately prior to surgery if ALL of the following criteria are met:

1. Prior to surgery the patient did not have AEs or progression which necessitated dabrafenib or trametinib cessation.
2. The patient has recovered from surgery without unexpected complication.
3. At least 1 week has passed since surgery.
4. The patient has evaluable residual tumor.
5. No more than 6 weeks has elapsed since surgery.

Patients whose disease is judged to be not amenable to resection will continue dabrafenib and trametinib indefinitely as long as there has not been tumor progression either by RECIST v1.1 or clinical progression criteria, there have not been unacceptable adverse events and the patient has not decided to discontinue for other reasons.

Clinical evaluations for protocol purposes will take place according to the schedule defined in Section 9. Dose modifications will be according to the guidelines in Section 6.

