7.2 Adverse Event Reporting

For detailed guidance on reporting adverse events, refer to the adverse event SOP (Appendix B)

Reporting

To ensure patient safety, every SAE, regardless of suspected causality, occurring after the patient has provided the main informed consent and until at least 30 days after the patient has stopped study treatment must be reported to Novartis within 24 hours of learning of its occurrence.

Any SAEs experienced after this 30 days period should only be reported to Novartis if the investigator suspects a causal relationship to the study treatment. Recurrent episodes, complications, or progression of the initial SAE must be reported as follow-up to the original episode within 24 hours of the investigator receiving the follow-up information. An SAE occurring at a different time interval or otherwise considered completely unrelated to a previously reported one should be reported separately as a new event.

Information about all SAEs is collected and recorded on the Serious Adverse Event Report Form; all applicable sections of the form must be completed in order to provide a clinically thorough report. The investigator must assess and record the relationship of each SAE to each specific study treatment (if there is more than one study treatment), complete the SAE Report Form in English, and send the completed, signed form by fax within 24 hours to the oncology Novartis Drug Safety and Epidemiology (DS&E) department - [contact]). The original copy of the SAE Report Form and the fax confirmation sheet must be kept with the case report form documentation at the study site. Follow-up information is sent to the same contact(s) to whom the original SAE Report Form was sent, using a new SAE Report Form stating that this is a follow-up to the previously reported SAE and giving the date of the original report. Each re-occurrence, complication, or progression of the original event should be reported as a follow-up to that event regardless of when it occurs. The follow-up information should describe whether the event has resolved or continues, if and how it was treated, whether the blind was broken or not, and whether the patient continued or withdrew from study participation.

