If the SAE is not previously documented in the Investigator's Brochure or Package Insert (new occurrence) and is thought to be related to the Novartis study treatment, an oncology Novartis Drug Safety and Epidemiology (DS&E) department associate may urgently require further information from the investigator for Health Authority reporting. Novartis may need to issue an Investigator Notification (IN), to inform all investigators involved in any study with the same drug that this SAE has been reported. Suspected Unexpected Serious Adverse Reactions (SUSARs) will be collected and reported to the competent authorities and relevant ethics committees in accordance with Directive 2001/20/EC or as per national regulatory requirements in participating countries.

Pregnancies

To ensure patient safety, each pregnancy occurring while the patient is on study treatment must be reported to Novartis within 24 hours of learning of its occurrence. The pregnancy should be followed up to determine outcome, including spontaneous or voluntary termination, details of the birth, and the presence or absence of any birth defects, congenital abnormalities, or maternal and/or newborn complications.

Pregnancy should be recorded on a Clinical Trial Pregnancy Form and reported by the investigator to the oncology Novartis Drug Safety and Epidemiology Department (DS&E). Pregnancy follow-up should be recorded on the same form and should include an assessment of the possible relationship to the study treatment any pregnancy outcome. Any SAE experienced during pregnancy must be reported on the SAE Report Form.

Adverse events will be graded according to CTCAE v4.03. Both Serious and Non-Serious Adverse Events will be clearly noted in source documentation and listed on study specific Case Report Forms (CRFs). The Protocol Director (PD) or designee will assess each

Adverse Event (AE) to determine whether it is unexpected according to Section 7.1 of the protocol and related to dabrafenib and trametinib.

SAEs and all subsequent follow-up reports will be reported to the CCTO Safety Office regardless of the event's relatedness to the investigation. Following review by the CCTO Safety Officers, any events meeting the IRB definition of "Unanticipated Problem" will be reported to the IRB using eProtocol within 10 working days of the review, or within 5 working days for deaths or life-threatening experiences. **SAEs will be relayed back to Novartis.**

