7.3 Pregnancy

Pregnancy Testing and Prevention

The need for a screening pregnancy test depends on whether a female subject is of childbearing potential or non-childbearing potential.

A female of non-childbearing potential (ie, physiologically incapable of becoming pregnant) is defined as any female who has had a hysterectomy, bilateral oophorectomy (ovariectomy), bilateral tubal ligation or tubal occlusion, or is post-menopausal.

A practical definition accepts menopause after 1 year without menses with an appropriate clinical profile, eg, age appropriate, > 45 years in the absence of hormone-replacement therapy (HRT). In questionable cases, the subject must have a follicle-stimulating hormone (FSH) value > 40 mIU/mL and an estradiol value < 40 pg/mL (< 140 pmol/L).

A female of child-bearing potential is defined as any female who does not meet the criteria of non-childbearing potential as described in the previous paragraph.

If a female subject is of childbearing potential, she must have a serum β -human chorionic gonadotropin (HCG) pregnancy test performed within 14 days prior to randomization. Subjects with a positive pregnancy test result must be excluded from the study. Subjects with a negative pregnancy test result must agree to use an effective contraception method as described below throughout study treatment and until 4 months after the last dose of study treatment.

Novartis acceptable contraceptive methods, when used consistently and in accordance with both the product label and the instructions of the physician, are as follows:

- An intrauterine device with a documented failure rate of less than 1% per year.
- Male partner sterilization prior to the female subject's entry, and this male is the sole sexual partner for that female.
- Complete abstinence from sexual intercourse for 14 days prior to enrollment, throughout study treatment, and for at least 4 months after the last dose of study treatment. Abstinence is only acceptable when in line with the preferred and usual lifestyle of the subject. Periodic abstinence (eg, calendar, ovulation, symptothermal, post-ovulation methods, etc) and withdrawal are not acceptable methods of contraception.
- Double-barrier contraception: condom and occlusive cap (diaphragm or cervical/vault caps) with a vaginal spermicidal agent (foam/gel/cream/suppository).

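### Mandatory pregnancy reporting in Section 7.2 stops with study treatment, although the protocol requires contraception for months after the last dose

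*Combined protocol and SAP*

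**What the plan says.** **Reporting.** Under the Pregnancies heading of Section 7.2, "each pregnancy occurring while the patient is on study treatment must be reported to Novartis within 24 hours of learning of its occurrence". The pregnancy is then followed to its outcome, including any birth defect and any maternal or newborn complication, and recorded on a dedicated pregnancy form. No period after treatment is named. The end of Section 7.3, on what to do when a subject becomes pregnant, likewise speaks only of the treatment period.

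**Contraception.** Three places set a period after treatment, and they differ:
- Section 3.1, inclusion criterion 8: patients of childbearing potential "must agree to use effective contraception until at least 6 months after treatment with dabrafenib and trametinib".
- Section 3.1, exclusion criterion 8: effective contraception "throughout the treatment period and for 4 to 6 months after the last dose of study treatment".
- Section 7.3: contraception "throughout study treatment and until 4 months after the last dose of study treatment".

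**Treatment length.** Under Section 4.0, patients with resectable tumors "will continue dosing continuously for at least 6 weeks and proceed to surgery between weeks 6 and 7, without dose interruption". After that, "Patients whose tumors are grossly completely resected will not resume dabrafenib and trametinib". Incompletely resected patients may resume if listed conditions are met. By contrast, "Patients whose disease is judged to be not amenable to resection will continue dabrafenib and trametinib indefinitely", subject to progression, adverse events and patient choice.

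**SAEs.** Section 7.2 requires every SAE, whatever its cause, to be reported to Novartis until at least 30 days after treatment stops. Beyond that, "Any SAEs experienced after this 30 days period should only be reported to Novartis if the investigator suspects a causal relationship to the study treatment". Section 7.2.1 counts a congenital anomaly or birth defect as an SAE. Pregnancy itself is not on that list.

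**The concern.** The protocol treats the months after the last dose as a time when conception should be avoided, but it does not ask sites to report or follow a conception in those months. The two windows start together and end at different points. The mismatch is largest in completely resected patients, who take the drugs for a few weeks and then carry a contraception requirement lasting several months.

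What is at stake is safety information: the course and outcome of pregnancies conceived soon after exposure, at a time the protocol itself considers sensitive. Pregnancy also has a shorter mandatory window than an ordinary SAE, which has a tail of at least 30 days. Nothing visible in the protocol prompts detection either. The study calendar in Section 9 lists a pregnancy test only before the study, and Section 4.2 follows protocol-related adverse events for 4 weeks after the last dabrafenib dose.

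**Working it through.** The plan gives no figure for this point, so there is none to reproduce. The check is a comparison of windows.

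**Inputs**
- Time on drug, completely resected patients: T = 6 to 7 weeks (Section 4.0).
- Contraception after the last dose: C = 4 months (Section 7.3) to 6 months (the minimum in inclusion criterion 8; the upper end in exclusion criterion 8).
- Conversion: 1 month = 365.25 / 12 / 7 = 4.35 weeks. So 4 months = 17.4 weeks and 6 months = 26.1 weeks.

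**Formula.** Share of calendar time, from first dose to the end of required contraception, that lies outside the pregnancy-reporting rule = C / (T + C).

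**Completely resected patients**

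| C | T = 7 weeks | T = 6 weeks |
|---|---|---|
| 17.4 weeks | 17.4 / 24.4 = 71% | 17.4 / 23.4 = 74% |
| 26.1 weeks | 26.1 / 33.1 = 79% | 26.1 / 32.1 = 81% |

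Exclusion criterion 8 also asks for 14 days of contraception before enrollment. Adding those 2 weeks to the denominator gives 17.4 / 26.4 = 66% at the low end and 26.1 / 34.1 = 77% at the high end.

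**Patients treated longer.** The protocol sets no duration, so T is assumed:

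| Assumed T | C = 17.4 weeks | C = 26.1 weeks |
|---|---|---|
| 12 weeks | 59% | 68% |
| 26 weeks | 40% | 50% |
| 52 weeks | 17.4 / 69.4 = 25% | 26.1 / 78.1 = 33% |
| 104 weeks | 14% | 20% |

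The share exceeds one half only while T is shorter than C, that is, for treatment under about 4 or 6 months. The uncovered stretch itself is the same 4 to 6 months for everyone.

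**What the SAE rule covers.** The any-cause tail of 30 days is 30 / 7 = 4.3 weeks. Of the period after treatment, (17.4 − 4.3) / 17.4 = 75% to (26.1 − 4.3) / 26.1 = 84% falls later, when a serious event goes to Novartis under that rule only if causality is suspected. A birth from a conception after the last dose would fall well beyond day 30. A birth defect would therefore depend on that judgement, and on the site learning of an outcome it had no duty to follow.

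**The case against.** The strongest case against is that the gap is narrower than it looks, and much of that case stands.

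- A reader might infer that no other rule captures anything after treatment. That is not so. Birth defects, hospitalizations and medically significant events are SAEs under Section 7.2.1 and have the reporting route described above. Section 7.2 also sends SAEs to the institution's safety office regardless of relatedness, with no end date stated there. What remains uncovered is the pregnancy itself and its routine follow-up, plus, as far as Novartis is concerned, late serious events judged unrelated.
- A reader might infer that fetal exposure during pre-surgical dosing goes unrecorded. It does not. A pregnancy that began on treatment is covered even if discovered after surgery, because the 24 hours run from learning of it. Only conceptions after the last dose fall outside.
- A reader might take 71% to 81% as a share of risk, or as applying to all patients. It is neither. It weights every week equally, for which the documents give no basis, and it applies to short treatment only. The proportion of patients who will be completely resected is not stated.
- Section 7.2 refers to an adverse event SOP through Appendix B. Its text is not in the documents, and it could contain a pregnancy rule that extends past treatment.
- Pregnancy is not an analyzed outcome. Section 12.5 plans CTCAE tables, review of SAEs and treatment completion rates, so a claim that the safety conclusion would be incomplete goes too far.

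None of this removes the mismatch in the protocol's own text. The pregnancy sentence in Section 7.2 is explicit, and a site that follows it exactly need not report a conception that falls inside the required contraception period.

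**Conclusion.** The point holds as a mismatch between two windows. Pregnancies conceived after the last dose, but while contraception is still required, are outside mandatory reporting and follow-up. The uncovered stretch is 4 to 6 months, and longer if the 6-month minimum in inclusion criterion 8 is exceeded. This is most of the calendar window for completely resected patients and a minority of it for patients treated for a year or more.

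The conclusion assumes that the SOP behind Appendix B adds no rule of its own and that resected patients have surgery in the planned interval. The absolute effect is likely to be small: Section 12.3 caps enrollment at 21, only some of these patients will be of childbearing potential, and those patients must agree to contraception over the same months. The response-rate analysis and its operating characteristics are untouched. It is a low-cost safety improvement worth making, not a defect that threatens the trial's conclusions.

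**What to change.** Amend the pregnancy rule in Section 7.2 so that each pregnancy occurring from the first dose until the end of the required post-treatment contraception period is reported within 24 hours of the site learning of it and followed to outcome.

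Before that, reconcile inclusion criterion 8, exclusion criterion 8 and Section 7.3, which state different contraception periods. The choice of length is the sponsor's. The reporting window should refer to that single period rather than repeat a number, so that the two cannot diverge again. The sponsor should also check that the SOP cited in Appendix B agrees.

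For a completely resected patient, the reporting window would grow from 6 to 7 weeks to 23.4 to 24.4 weeks if the period is 4 months, or to 32.1 to 33.1 weeks if it is 6 months. The uncovered share would fall to zero.

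The cost is one amended sentence and a line in the reporting instructions. The pregnancy form and the follow-up process already exist. The downside is that sites must ask about pregnancy for some months after treatment in patients of childbearing potential. Section 6.2.6 already plans skin monitoring every 2 months for 6 months after dabrafenib stops, unless another anti-neoplastic therapy begins, so many of these contacts are foreseen.

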7.2.1 SAE definitions

Serious adverse event (SAE) is defined as one of the following:

- Is fatal or life-threatening
- Results in persistent or significant disability/incapacity
- Constitutes a congenital anomaly/birth defect
- Is medically significant, ie, defined as an event that jeopardizes the patient or may require medical or surgical intervention to prevent one of the outcomes listed above
- Requires inpatient hospitalization or prolongation of existing hospitalization,

Note that hospitalizations for the following reasons should not be reported as serious adverse events:

- Routine treatment or monitoring of the studied indication, not associated with any deterioration in condition
- Elective or pre-planned treatment for a pre-existing condition that is unrelated to the indication under study and has not worsened since signing the informed consent
- Social reasons and respite care in the absence of any deterioration in the patient's general condition

Note that treatment on an emergency outpatient basis that does not result in hospital admission and involves an event not fulfilling any of the definitions of a SAE given above is not a serious adverse event

7.3 Pregnancy

Pregnancy Testing and Prevention

The need for a screening pregnancy test depends on whether a female subject is of childbearing potential or non-childbearing potential.

A female of non-childbearing potential (ie, physiologically incapable of becoming pregnant) is defined as any female who has had a hysterectomy, bilateral oophorectomy (ovariectomy), bilateral tubal ligation or tubal occlusion, or is post-menopausal.

A practical definition accepts menopause after 1 year without menses with an appropriate clinical profile, eg, age appropriate, > 45 years in the absence of hormone-replacement therapy (HRT). In questionable cases, the subject must have a follicle-stimulating hormone (FSH) value > 40 mIU/mL and an estradiol value < 40 pg/mL (< 140 pmol/L).

A female of child-bearing potential is defined as any female who does not meet the criteria of non-childbearing potential as described in the previous paragraph.

If a female subject is of childbearing potential, she must have a serum β -human chorionic gonadotropin (HCG) pregnancy test performed within 14 days prior to randomization. Subjects with a positive pregnancy test result must be excluded from the study. Subjects with a negative pregnancy test result must agree to use an effective contraception method as described below throughout study treatment and until 4 months after the last dose of study treatment.

Novartis acceptable contraceptive methods, when used consistently and in accordance with both the product label and the instructions of the physician, are as follows:

- An intrauterine device with a documented failure rate of less than 1% per year.
- Male partner sterilization prior to the female subject's entry, and this male is the sole sexual partner for that female.
- Complete abstinence from sexual intercourse for 14 days prior to enrollment, throughout study treatment, and for at least 4 months after the last dose of study treatment. Abstinence is only acceptable when in line with the preferred and usual lifestyle of the subject. Periodic abstinence (eg, calendar, ovulation, symptothermal, post-ovulation methods, etc) and withdrawal are not acceptable methods of contraception.
- Double-barrier contraception: condom and occlusive cap (diaphragm or cervical/vault caps) with a vaginal spermicidal agent (foam/gel/cream/suppository).

Note: Hormonal-based methods (eg, oral contraceptives) are not permitted as contraception due to potential drug-drug interactions with dabrafenib.

Female subjects who are lactating must discontinue nursing prior to the first dose of study treatment and must refrain from nursing throughout the treatment period and for 4 months following the last dose of study treatment.

If a subject becomes pregnant during the treatment period of the study, the study treatments should be stopped immediately.

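### The protocol gives three different post-treatment contraception periods for women of childbearing potential (at least 6 months, 4 to 6 months, 4 months) and does not say which governs

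*Combined protocol and SAP*

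**What the plan says.** The post-treatment contraception period is stated in three places.

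- **Section 3.1, inclusion criterion 8:** "Patients of childbearing potential must agree to use effective contraception until at least 6 months after treatment with dabrafenib and trametinib". The criterion then points the reader onward: "See exclusion criteria re pregnancy testing".
- **Section 3.1, exclusion criterion 8:** women of childbearing potential must agree to effective contraception for 14 days before enrolment, "throughout the treatment period and for 4 to 6 months after the last dose of study treatment".
- **Section 7.3:** women with a negative pregnancy test must agree to an effective method "throughout study treatment and until 4 months after the last dose of study treatment". The abstinence option in the same section is worded as a minimum: "throughout study treatment, and for at least 4 months after the last dose of study treatment".

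Section 7.3 also gives a 4-month period for refraining from nursing. That is a separate rule and is not counted here.

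**The concern.** One safeguard for one group of patients should have one duration. Here it has three, and two of them sit in the same checklist, which must be completed and signed before registration. A range of 4 to 6 months also gives no single end date and does not say what decides between its two ends.

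The instruction carries weight in this trial. Under Section 4.0, patients with resectable tumors have surgery between weeks 6 and 7 and do not resume the drugs if the tumor is grossly completely removed. For them the contraception period after treatment is longer than treatment itself.

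The protocol also shows little later backstop. The calendar in Section 9 lists pregnancy testing only before the study. Section 7.2 requires reporting of pregnancies that occur on study treatment. Section 4.2 follows adverse events for 4 weeks after the last dabrafenib dose. Counselling is therefore the main protection in the months where the texts disagree.

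**Working it through.** No formula applies, and the plan gives no calculated figure to reproduce. The check sets the texts side by side and asks what agreement from a patient would satisfy each.

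**Inputs**

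| Place | Who | Post-treatment period | Counted from |
|---|---|---|---|
| Section 3.1, inclusion 8 | patients of childbearing potential | at least 6 months | treatment with the two drugs |
| Section 3.1, exclusion 8 | women of childbearing potential | 4 to 6 months | last dose of study treatment |
| Section 7.3, general rule | female subjects of childbearing potential | 4 months | last dose of study treatment |
| Section 7.3, abstinence option | same | at least 4 months | last dose of study treatment |

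**Step 1: do the rules address the same people?** Yes, for women of childbearing potential. Inclusion criterion 8 says patients, the other two say women or female subjects, and inclusion criterion 8 refers the reader to the exclusion criteria on pregnancy testing. If its wording was meant to reach men as well, it still covers the women addressed by the other two.

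**Step 2: which agreements satisfy which text?**

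| Woman agrees to | Inclusion 8 | Exclusion 8 | Section 7.3 |
|---|---|---|---|
| 4 months | not met | met (lower end) | met |
| 5 months | not met | met (within range) | met, if 4 months is a minimum |
| 6 months | met | met (upper end) | met, if 4 months is a minimum |

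If the range in exclusion criterion 8 is read as bounded at both ends, the two entry criteria agree only at exactly 6 months. If it is read as a 4-month minimum, they agree at 6 months and beyond.

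**Step 3: size of the gap.** Minimum in inclusion criterion 8 less the period in Section 7.3: 6 − 4 = 2 months. Minimum in inclusion criterion 8 less the lower end of exclusion criterion 8: 6 − 4 = 2 months.

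**Step 4: does any text resolve it?** No statement of precedence was found. Nothing assigns the periods to different drugs, sexes or contraceptive methods.

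**Step 5: is the starting point clear?** Not fully. Inclusion criterion 8 counts from treatment with both drugs, and the other two count from the last dose of study treatment. Section 4.0 lets either drug continue after the other is permanently discontinued, so inclusion criterion 8 does not fix a date when the drugs stop at different times.

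**The case against.** The strongest reply is that the texts can all be met at once. Inclusion criterion 8 is an entry condition. Under Section 3.1 eligibility is verified by the coordinator, the treating physician and an independent reviewer, and under Section 11.3.1 it is confirmed centrally before enrolment. A reader who applies every criterion together arrives at 6 months. That period satisfies inclusion criterion 8, the upper end of exclusion criterion 8, and Section 7.3 if its 4 months is a minimum, as its abstinence option suggests.

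This limits the consequence but does not remove the contradiction. The protocol never says that the longest period governs, and the section devoted to pregnancy states the shortest.

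A reader might infer that women counselled from Section 7.3 would stop contraception too early. The documents do not support that. It assumes counselling from Section 7.3 alone, although inclusion criterion 8 is checked at entry. A reader might also infer that patients are being told the shorter period. That cannot be established: the consent form is not in the reviewed document, and Appendix A says the patient drug guides are attached to the ethics application. The patient-facing text may already give a single period.

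It is also fair to say that a 4-to-6-month range can be read as a 4-month minimum. On that reading the range can be followed, and its defect is that its lower end conflicts with inclusion criterion 8.

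**Conclusion.** The inconsistency stands, and the protocol is wrong as written on this point. A site that follows Section 7.3 could accept and counsel a period up to 2 months shorter than the entry criterion demands. Two sites could give different advice while each follows the document, and Section 11.1 does not allow a site to correct the text on its own.

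The conclusion rests on the protocol wording alone. It assumes nothing about what patients have been told. The number affected is unknown: Section 12.3 plans 11 to 21 patients, and the documents do not say how many would be women of childbearing potential. Which duration is right is not judged here. There is no effect on the primary endpoint, the sample size or the error rates of the two-stage design. The point should be corrected because it concerns fetal safety and eligibility.

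**What to change.** Reconcile inclusion criterion 8, exclusion criterion 8 and Section 7.3 (both its general rule and its abstinence option) to one stated duration with one stated starting point. The sponsor chooses both. The starting point should be worded so that it gives a definite date when the two drugs are stopped at different times. State also whether inclusion criterion 8 is meant to reach anyone beyond women of childbearing potential. Then check the consent form and any other patient-facing text drawn from these places against the reconciled wording.

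The cost is a wording amendment, with the review-board approvals at all sites that Section 11.1 already requires for any change. No design figure or analysis changes.
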